1. Two or more serial chest radiographs with at least 1 of the following (*in patients without underlying pulmonary or cardiac disease [eg, respiratory distress syndrome, bronchopulmonary dysplasia, pulmonary edema, or chronic obstructive pulmonary disease], 1 definitive chest radiograph is acceptable*):
 - New or progressive and persistent infiltrate
 - Consolidation
 - Cavitation
2. At least 1 of the following:
 - Fever ($>38^{\circ}\text{C}$ or $>100.4^{\circ}\text{F}$)
 - Leukopenia (<4000 WBC/ mm^3) or leukocytosis ($\geq 12,000$ WBC/ mm^3)
 - For adults ≥ 70 years old, altered mental status with no other recognized cause

AND at least 2 of the following:

 - New onset of purulent sputum, or change in character of sputum, or increased respiratory secretions, or increased suctioning requirements
 - New-onset or worsening cough, or dyspnea or tachypnea
 - Rales or bronchial breath sounds
 - Worsening gas exchange (eg, O_2 desaturations [eg, $\text{PaO}_2/\text{FiO}_2 \leq 240$], increased oxygen requirements, or increased ventilator demand)

Microbiologically confirmed pneumonia must demonstrate at least 1 of the following criteria:

- Positive growth in blood culture not related to another source of infection
- Positive growth in culture of pleural fluid
- Positive quantitative culture from minimally contaminated lower respiratory tract (LRT) specimen (eg, bronchial alveolar lavage or protected specimen brushing)

Microbiological Classification

Confirmed pneumonia cases are to be classified as

- **Microbiologically confirmed *S aureus* pneumonia** if the subject has *S aureus* cultured from blood, pleural fluid, and/or minimally contaminated LRT specimen, as per microbiologically confirmed pneumonia criteria
- **Microbiologically confirmed non-*S aureus* pneumonia** if the subject has only non-*S aureus* organism(s) cultured from blood, pleural fluid, and/or minimally contaminated LRT specimen, as per microbiologically confirmed pneumonia criteria
- **Non-microbiologically confirmed pneumonia** if the above criteria for microbiologically confirmed pneumonia are not met

SURGICAL-SITE INFECTIONS

SUPERFICIAL SSI

Clinical Criteria

Confirmed superficial SSI must meet the following criteria:

1. Involves only skin and subcutaneous tissue of the incision
AND
2. Patient has at least 1 of the following:
 - a. Purulent drainage from the superficial incision
 - b. Organisms isolated from an aseptically obtained culture of fluid or tissue from the superficial incision
 - c. Superficial incision that is deliberately opened by a surgeon or attending physician or designee and is culture-positive or not cultured (a culture-negative finding does not meet this criterion)

AND At least 1 of the following signs or symptoms of infection:

- pain or tenderness
 - localized swelling
 - redness
 - heat
- d. Diagnosis of a superficial incisional SSI by the surgeon or attending physician or designee

Microbiological Classification

Confirmed superficial SSI cases are to be classified as

- **Microbiologically confirmed *S aureus* superficial SSI** if the subject has *S aureus* cultured from an aseptically obtained culture of fluid or tissue from the superficial incision, or from a superficial incision that is deliberately opened, as part of clinical criterion 2
- **Microbiologically confirmed non-*S aureus* superficial SSI** if the subject has only non-*S aureus* organism(s) cultured from an aseptically obtained culture of fluid or tissue from the superficial incision, or from a superficial incision that is deliberately opened, as part of clinical criterion 2
- **Non-microbiologically confirmed superficial SSI** if the above criteria for microbiologically confirmed superficial SSI are not met

DEEP INCISIONAL SSI

– *Clinical Criteria*

Confirmed deep incisional SSI must meet the following criteria:

1. Involves deep soft tissues of the incision (eg, fascial and muscle layers)

AND

2. Patient has at least *1* of the following:

- a. Purulent drainage from the deep incision
- b. A deep incision that spontaneously dehisces or is deliberately opened by a surgeon, attending physician or designee and is culture-positive or not cultured (culture-negative finding does not meet this criterion)

AND the patient has at least *1* of the following signs or symptoms:

- fever (>38°C or >100.4°F)
 - localized pain or tenderness
- c. An abscess or other evidence of infection involving the deep incision that is found on direct examination, during invasive procedure, or by histopathologic examination or imaging test.

Microbiological Classification

Confirmed deep incisional SSI cases are to be classified as:

- **Microbiologically confirmed *S aureus* deep incisional SSI** if the subject has a deep incision that spontaneously dehisces or is deliberately opened by a surgeon, attending physician or designee and is culture-positive for *S aureus* as part of clinical criterion 2
- **Microbiologically confirmed non-*S aureus* deep incisional SSI** if the subject has a deep incision that spontaneously dehisces or is deliberately opened by a surgeon, attending physician or designee and is culture-positive for only non-*S aureus* organism(s), as part of clinical criterion 2
- **Non-microbiologically confirmed deep incisional SSI** if the above criteria for microbiologically confirmed deep incisional SSI are not met

ORGAN SPACE SURGICAL SITE INFECTION

– Clinical Criteria

Confirmed organ space SSI must meet the following criteria:

1. Infection involves any part of the body, excluding the skin incision, fascia, or muscle layers, that is opened or manipulated during the operative procedure

AND

2. Patient has at least *1* of the following:

- a. Purulent drainage from a drain that is placed into the organ/space
- b. Organisms isolated from an aseptically obtained culture of fluid or tissue in the organ/space
- c. An abscess or other evidence of infection involving the organ/space that is found on direct examination, during invasive procedure, or by histopathologic examination or imaging test

AND

3. Meets at least *1* criterion for an organ/space infection site listed below:

- Osteomyelitis
- Vertebral disc space infection
- Meningitis
- Spinal abscess without meningitis
- Intra-abdominal infection
- Joint or bursa infection

Microbiological Classification

Confirmed organ/space SSI cases are to be classified as

- **Microbiologically confirmed *S aureus* organ/space SSI** if the subject has *S aureus* organisms isolated from an aseptically obtained culture of fluid or tissue in the organ/space, as part of clinical criterion 2
- **Microbiologically confirmed non-*S aureus* organ/space SSI** if the subject has only non-*S aureus* organisms isolated from an aseptically obtained culture of fluid or tissue in the organ/space, as part of clinical criterion 2
- **Non-microbiologically confirmed organ/space SSI** if the above criteria for microbiologically confirmed organ space SSI are not met

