6.4.2. BSI/SSI Assessment Visit

At any time after surgery until completion of study participation, when a subject is suspected of having a BSI and/or SSI, a BSI/SSI assessment visit will be conducted.

If the BSI/SSI assessment visit occurs during the index study admission, or is coincident with the Day 21 telephone contact or the Day 42, Day 90, or Day 180 postoperative assessment visit, the BSI/SSI assessment visit study procedures common to both visits may be combined.

The following procedures will be conducted:

- Complete a PDI event report for BSI and /or SSI, as appropriate for the PDI(s), as described in [Section 7.1.1](#).
- Collect and process a blood sample of approximately 24 mL for immunogenicity assessments.
- Collect colonization swab samples from the nose and throat.

- Collect blood culture sample(s) for any suspected BSI or deep incisional or organ/space SSI and, when clinically indicated, for a superficial SSI.
- For an SSI that is operatively incised and/or spontaneously draining, collect a wound culture swab as per local clinical laboratory guidance. Where possible, tissue and fluid samples are to be taken prior to commencing administration of antibiotics.
- Record antibiotic therapy as concomitant medication(s) as described in [Section 5.4](#).
- Determine whether any AEs or SAEs have occurred or require updating since the last subject assessment. Record and report AEs as described in [Section 8](#) and according to the Schedule of Activities for Adverse and Study Event Reporting (Table 2).
- Complete the source documents and CRF.

In the event that a subject is identified as having a suspected BSI and/or SSI and it is not possible to complete the BSI/SSI assessment visit (eg, in the event that the investigator is made aware of an infection that has already been treated to resolution by medical personnel external to the study team, and where there are no active signs or symptoms of infection), a PDI event report will be completed regardless.

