9.3. Efficacy Analysis

The per-protocol population will be the primary population for analysis of all efficacy objectives. Efficacy objectives will also be assessed using the modified intent-to-treat (mITT) populations. Subgroup analyses will be performed on both the per-protocol and the mITT populations.

All analyses for the SSI endpoints assume 100% correct classification of suspected *S aureus* cases, ie, no cases are missed and no noncases are included in the statistical analysis. All primary and secondary efficacy analyses will be repeated for sex, race, ethnicity, and age subgroups.

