Endpoint definitions include specified microbiological confirmations. Absence of microbiological confirmation excludes the suspected infection from the endpoint analysis. But if the microbiological tests are not performed (because of lack of sample, lost sample, invalid assay, etc), then the PDI will be considered a missing value for endpoint analyses. PDIs adjudicated as noncases in the presence of sufficient and valid microbiological testing will not be considered missing values. Missing-data sensitivity analyses will be performed for the BSI, SSI, and ISA disease endpoints. The methods for missing-data sensitivity analyses are described in [Handling of Missing Values](#).

Another set of sensitivity analyses will incorporate follow-up time in the efficacy calculation. The variable P will be the proportion of SA4Ag cases divided by the number of all cases. The variable h will be ratio of total follow-up time in the placebo group to the total follow-up time in the SA4Ag group. Follow-up time for any subject is the date of study completion (or dropout or case onset, whichever comes first) minus the date of index surgery, plus 1. Then estimated efficacy will be  $1-hP/(1-P)$ . The efficacy's CI will be obtained by calculating the CI for P, then substituting in the expression. The CI for P will be obtained using the Clopper-Pearson method. The confidence level will be the same as for the indicated endpoint. The method is described in Blackwelder, substituting follow-up time for number of subjects. Follow-up time sensitivity analyses will be performed for the primary and secondary endpoints in both the mITT and PP efficacy populations.

Number needed to treat (NNT) will be calculated as the reciprocal of the proportion of SA4Ag cases minus the proportion of placebo cases. NNT will be calculated for each endpoint. A 95% CI will be obtained for each NNT by obtaining a 2-sided 95% CI on the difference in proportions using the method of Chan and Zhang, then reciprocating the upper and lower limits.

1. If the difference in proportions and both confidence limits are less than zero, then the results will be presented as  $NNT = xx.x (xx.x, xx.x)$ , with the negative signs omitted.

2. If the difference in proportions and both confidence limits are greater than zero, then the results will be presented as number needed to harm (NNH) = xx.x (xx.x, xx.x).

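### S aureus grown from an unopened deep incisional infection has no route to confirmation in Appendix 1, so the event leaves the efficacy endpoints and the subject may be eligible as a control

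*Protocol*

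**What the plan says.** Protocol Appendix 1 (Deep Incisional SSI) requires deep soft-tissue involvement plus at least one of three findings. Finding 2a is "Purulent drainage from the deep incision". Finding 2b is an incision that dehisces or is opened, is culture-positive or not cultured, and comes with fever or local pain or tenderness. Finding 2c is "An abscess or other evidence of infection involving the deep incision that is found on direct examination, during invasive procedure, or by histopathologic examination", or on imaging.

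The microbiological classification beneath these criteria is narrower. It recognises S aureus in one situation only: "if the subject has a deep incision that spontaneously dehisces or is deliberately opened by a surgeon, attending physician or designee and is culture-positive", with S aureus the organism grown; the wording ties this to criterion 2. The non-S aureus class carries the same condition. An infection is non-microbiologically confirmed "if the above criteria for microbiologically confirmed deep incisional SSI are not met".

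The two neighbouring rules go by specimen. Organ/space SSI is S aureus when there are S aureus "organisms isolated from an aseptically obtained culture of fluid or tissue in the organ/space, as part of clinical criterion 2". Superficial SSI accepts an aseptic culture of fluid or tissue, or a positive culture from an opened incision.

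On sampling, Protocol Section 6.4.2 says: "For an SSI that is operatively incised and/or spontaneously draining, collect a wound culture swab as per local clinical laboratory guidance". Section 7.3.3 adds cultures at any drainage procedure. Section 7.1.1.1 has the EAC confirm that the Appendix 1 clinical and microbiological criteria are met. SAP Section 8.1.1 drops infections without microbiological confirmation, treats them as missing only when the tests were not performed, and states: "PDIs adjudicated as noncases in the presence of sufficient and valid microbiological testing will not be considered missing values".

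**The concern.** A deep incisional infection can be clinically confirmed and have S aureus in a properly taken specimen, yet be recorded as lacking microbiological confirmation because of the state of the incision. Deep incisional SSI is a component of the primary endpoint, and the same class feeds the 180-day and the S aureus SSI secondary endpoints. No planned analysis brings such an event back.

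The problem outlasts the futility stop of December 2018. The nested case-control study uses the same adjudicated status to decide who is a case and who may be a control. Its purpose is to understand why the vaccine did not appear to protect. A control who in fact had a deep S aureus infection would blur the contrast it is meant to measure.

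**Working it through.** **1. Follow four culture-positive deep infections through the rule.** Each involves deep soft tissue and grows S aureus.

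| Presentation | Clinical route | Deep incisional class | Counts for the primary endpoint? |
|---|---|---|---|
| Incision dehisces or is opened; culture positive | 2b, or 2a/2c with opening | S aureus | Yes |
| Abscess first seen on imaging; incision later opened; culture positive | 2c | S aureus | Yes |
| Subfascial abscess aspirated through the skin; incision intact | 2c | Non-microbiologically confirmed | Only through a qualifying BSI or organ/space SSI |
| Pus drains; swab positive; incision not opened | 2a | Depends on whether drainage is read as dehiscence, which is undefined | Unclear |

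The closing reference to criterion 2 does not rescue row 3. It sits after the dehisced-or-opened condition and does not replace it.

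**2. Compare with the neighbours.** Move the row 3 specimen one layer deeper, into the organ/space, and the culture is accepted. Move it to the superficial layer and an aseptic fluid culture is again accepted. Only the middle layer rejects it.

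**3. Follow row 3 into the analyses.**
- SAP Section 8.1.1: testing was done and valid, so the event is a noncase and not missing.
- SAP Section 7: the best-case, worst-case, MAR and MNAR analyses cover only infections with insufficient testing, so row 3 is outside them.
- SAP Section 8.1.3.5: controls are per-protocol subjects at case sites who completed Visit 5 and had no adjudication-confirmed S aureus infection. Row 3 can meet that. The sensitivity analysis that removes controls with non-S aureus infections need not remove this subject.

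**4. Reproduce the design figures and see what moves.** Inputs are from Protocol Sections 9.1 and 9.2: 1:1 allocation, VE 20% (null) and 70% (alternative), reject at 3 or fewer of 24 or 14 or fewer of 48, placebo incidence about 1.4%, dropout 10%.
- Vaccine share of cases p = (1 − VE)/(2 − VE): 0.8/1.8 = 0.444 and 0.3/1.3 = 0.231 (plan: 0.444, 0.230).
- Exact two-look binomial without futility stopping: power 0.878 at VE 70% and type I error 0.0224 at VE 20%. With the futility rules: 0.876 and 0.0222 (plan: 0.88; SAP Table 11: 87.5% and 2.3%).
- Enrolment = 48/[0.014 × (2 − VE)/2]/0.9: 5861 at VE 70% and 5443 at VE 60% (plan: about 6000 and 5440).

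If a share f of true cases is lost equally in both arms, (1 − f) cancels from p. At 48 confirmed cases, type I error, power and VE are therefore unchanged.

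**5. Unequal loss.** Observed VE = 1 − (1 − VE)(1 − f_v)/(1 − f_p), where f_v and f_p are the shares lost on vaccine and placebo. The shares below are assumptions, because the documents give none.
- f_v = f_p = 10%: VE 20% and 70% are unchanged.
- f_v = 20%, f_p = 10%: 20% becomes 28.9% and 70% becomes 73.3%.
- f_v = 5%, f_p = 15%: 20% becomes 10.6% and 70% becomes 66.5%.

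**6. Enrolment cannot be signed.** Take f = 5% for illustration. If 1.4% is the incidence under a broader definition, 48 cases need 48/[0.014 × 0.65 × 0.95 × 0.9], or 6170 subjects. If 1.4% already reflects the current wording, a broader rule needs 5861 × 0.95, or 5568. The documents do not say where 1.4% comes from, so even the direction is open.

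**The case against.** The strongest reply is that very few events are touched, and it largely stands. Any 2a or 2c infection that is later opened and grows S aureus counts. Blood cultures are required for every suspected deep SSI (Protocol Sections 6.4.2 and 7.3.2), so some affected subjects will qualify through BSI. Others will qualify through organ/space SSI.

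A second reply is that Appendix 1 often ties classification to the criterion that contains a culture: disc space and joint infection use criterion 1 only, and the intra-abdominal class omits the drain-culture route. On that view the narrow rule favours specificity by design. It explains the pattern only in part. The disc and joint rules still accept tissue or fluid from the infected site, whereas the deep incisional rule sets a condition on the incision.

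Third, the adjudication charter was not available and may read the rule more broadly. Section 7.1.1.1 still binds the EAC to Appendix 1. Some affected events might also appear in the SAP's any-pathogen exploratory endpoints, or under the opening sentence of the ISA definition in Protocol Section 2.

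Three stronger readings do not hold:
- A reader might infer that all culture-positive drainage is lost. The Section 6.4.2 swab is not stated to be aseptically obtained, and drainage might be read as dehiscence, so that is not established.
- A reader might say that Protocol Section 9.3 is contradicted where it assumes that "no cases are missed and no noncases are included in the statistical analysis". That sentence concerns correct classification against the case definition. A narrow definition is not misclassification under itself.
- A reader might claim a delay to the 24- and 48-case analyses. Enrolment ceased on 20 December 2018 after futility was met (SAP Section 8.1.3.5), so there is no further accrual to delay.

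**Conclusion.** The gap is real on the text but narrow. It covers deep incisional infections with S aureus from an aseptically obtained specimen, in an incision that neither dehisced nor was opened, and with no qualifying BSI or organ/space SSI. These are left out of the primary and secondary endpoints, are not recovered by the missing-data analyses, and are not barred from the control pool.

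The number of such events is not given and is probably small. No stated sample-size, type I error or power figure is wrong. Bias in VE needs a loss that differs by arm, and the documents give no reason to expect one. The conclusion assumes that the EAC applied Appendix 1 as written.

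**What to change.** In the deep incisional classification, keep the dehisced-or-opened route and add a second one: S aureus grown from aseptically taken fluid or tissue of the deep incision, under criterion 2a, 2b or 2c. Make the same change in the non-S aureus class and align the EAC charter. State whether drainage alone counts as dehiscence.

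Because enrolment has stopped after an unblinded interim, do not redefine the primary endpoint. Instead:
- Have the EAC, still blinded, re-read every confirmed deep incisional SSI that is classed as non-microbiologically confirmed and has an S aureus-positive culture. Select these events by that rule alone, without reference to allocation.
- Report the primary and secondary endpoints with the reclassified events counted, as a supplementary sensitivity analysis, and give the number by arm.
- Exclude these subjects from the nested case-control control pool.

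The cost is a protocol and SAP amendment and a blinded re-read of what should be a few events. No new sampling is needed. The supplementary result will be post hoc and should be labelled so.

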Appendix 2. Preoperative Assessment

- American Society of Anesthesiologists (*ASA*) Physical Status Classification Score
- Source of admission (other healthcare facility)
- Wound site preparation method (clippers, shaving, etc)
- *S aureus* /MRSA carriage evaluation
- Decolonization therapy
 - Intranasal mupirocin
 - Chlorhexidine
 - Other

Appendix 3. Perioperative Assessment

- Skin preparation (eg, betadine, chlorhexidine)
- Surgical procedure performed (eg, posterior lumbar interbody fusion)
- Wound classification (eg, clean, clean contaminated, contaminated)
- Skin closure type (eg, staples, sutures, other)
- Primary incision site (eg, midline posterior, posterolateral)
- Secondary incision(s)
 - Spinal site(s) (anterior, endoscopic, etc.)
 - Graft donor site(s)
- Intervertebral level(s) fused (eg, lumbar 4 through thoracic 5)
- Implanted material (type and composition eg, rod, titanium)

- | Device Type | Composition |
|--------------------|--------------------|
| • Rods | • Titanium |
| • Plates | • Stainless steel |
| • Screws | • Other |
| • Cages | |
| • Other | |
- Graft type (eg, autograft, allograft, bone morphogenic protein, other)
 - Duration of surgery (knife to skin closure)
 - Surgical site drains, indwelling catheters

- Vancomycin powder application to wound
- Prophylactic antibiotic (name, start and stop time, date, and dose)
- Estimated blood loss (mL)
- Blood product transfusion (eg, whole blood, red blood cells, platelets, clotting factors, cryoprecipitate, white blood cells, immunoglobulins, albumin, and plasma) and origin (heterologous or autologous donation/ transfusion of whole blood or red blood cells)
- Postoperative patient temperature (°C or °F) (first recorded postoperative value on return to ward)

Appendix 4. Healthcare-Utilization Assessment

- Number of days in hospital
- Number of days in an intensive care unit
- Number of readmissions to hospital
- Number of reoperations
- Number of inpatient days in a rehabilitation facility after discharge
- Number of inpatient days in a skilled nursing care facility/nursing home after discharge
- Discharge disposition
 - Home
 - Rehabilitation
 - Skilled nursing care facility
 - Death
 - Other
- Number of rehabilitation/physical therapy visits as an outpatient
- Days of antibiotic use

